2.13 Biomarkers

As a project standard, Novartis will analyze only biomarkers collected in the clinical database. For exploratory markers, since the studies are not adequately powered to assess specific biomarker-related hypotheses, the goal of these exploratory statistical analyses should be considered as the generation of new scientific hypotheses. No adjustment for multiple comparisons is usually planned for exploratory analyses. Furthermore, additional post hoc exploratory assessments are expected and may be performed.

There may be circumstances when a decision is made to stop sample collection, or not perform or discontinue their analysis due to either practical or strategic reasons. Under such circumstances, the number of samples may be inadequate to perform a rigorous data analysis and the available data will only be listed and potentially summarized.

If not otherwise specified, the FAS will be used for all biomarker analyses on patients with biomarker data.

Exploratory biomarker objectives

- To characterize mutations in the BCR-ABL1 gene at Week 1 Day 1, upon confirmed loss of molecular response and/or at end of treatment and examine their association with molecular and cytogenetic response for asciminib vs bosutinib

- To understand biology of CML and bone marrow microenvironment on leukemic stem cells (LSCs) eradication, including patients' immunogenicity
- To assess clonal evolution during treatment with asciminib vs. bosutinib
- To evaluate soluble/inflammatory factors that correlate with response to asciminib vs. bosutinib treatment

Only some analyses for the first exploratory biomarker objective about BCR-ABL1 mutation listed above are described here and the results will be included in the respective CSRs. Additional analyses for this and other exploratory biomarker objectives will be described in separate analyses plans, with results reported separately.

List of biomarkers evaluated and the collection time points

The biomarkers evaluated in the study are listed in [Table 2-8](#) below.

Table 2-8 **Sample biomarker summary table**

Biomarker	Time point	Sample	Method
Immune markers PD-L1 and CD8	Screening and end of treatment	Bone marrow biopsy	Immunohistochemistry
Leukemic stem cells characterization	Screening, week 24 and end of treatment	Bone marrow aspirate	Flow cytometry
BCR-ABL1 gene mutation	W1D1 pre-dose and end of treatment. If mutation is present at baseline, then also every 12 weeks after baseline	Peripheral blood	Sanger Sequencing
Low level mutations in BCR-ABL1 gene	W1D1 pre-dose and end of treatment	Peripheral blood	Mass spectrometry and NGS
Circulating cytokines in plasma	W1D1 pre-dose, Week 48 and end of treatment	Peripheral blood	MSD and ELISA
Genetic variant analysis of the UGT2B7 and UGT2B17 gene	W1D1	Peripheral blood	Genechip

General data handling and preprocessing

For bone marrow samples the latest assessment during screening period will be used as the baseline value, while for blood samples the week 1 day 1 (W1D1) pre-dose assessment will be used as the baseline value.

When more than one biomarker data value are available for a subject at any time point, the mean of the replicate values will be used for all statistical analyses.

2.13.1 Somatic mutation biomarker data handling and analysis

Handling of somatic biomarker data

Overall, somatic mutation status (wild type or mutant) will be derived from the mutational status of the interrogated exons for the BCR-ABL1 gene by Sanger Sequencing. These may be non-exclusive and the presence of mutation across more than one exon will be reported in separate categories.

Mutation summary statistics

All somatic mutation data will be reported using counts and percentages by the mutation type in the form of contingency tables with the rows containing the different mutations assayed, and the treatment groups in the columns. All the mutation categories for a gene will also be aggregated into mutant, wild type or missing/unknown groups and counts/percentages will be reported by these three categories as well. A summary table will be presented for baseline mutations and another summary table for post-baseline new mutations (not present at baseline).

All the mutation data will be listed for each subject ordered by treatment group.

Association between biomarkers and clinical outcome

This analysis does not adjust for multiple comparisons and results may have higher false positive rates.

The relationship between Week 1 Day 1 BCR-ABL1 gene mutation data (wild type or mutant) and outcome data (with or without MMR at and by 24 and 96 weeks using FAS, with or without CCyR at and by 24 and 96 weeks using CCyR analysis set) will be explored by reporting contingency tables and by applying a logistic regression including treatment group, Week 1 Day 1 BCR-ABL1 gene mutation and their interaction as covariates. Treatment group will be included in this summary table.

In addition, the same analysis will be performed for

- the relationship between post-baseline new BCR-ABL1 mutation (with or without new mutation) up to 48 weeks and outcome data (with or without MMR at 48 and 96 weeks using FAS, with or without CCyR at 48 and 96 weeks using CCyR analysis set).
- the relationship between post-baseline new BCR-ABL1 mutation (with or without new mutation) up to end of treatment and outcome data (with or without MMR at 96 weeks using FAS, with or without CCyR at 96 weeks using CCyR analysis set).

The odds ratios between treatment groups with 95% confidence intervals will be reported, for each biomarker category and overall. If treatment by biomarker interaction is significant (e.g. when $p < 0.1$), overall odds ratio for treatment will not be reported.

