To assess the impact of mistratifications on the treatment effect assessment, the same analysis will be repeated, adjusting for major cytogenetic status at baseline based on CRF data instead of based on randomization data.

Influence of early molecular response levels on long term molecular response levels

The relationship between MMR status at 24 weeks and MMR status at 48 and 96 weeks will be explored using FAS by reporting contingency tables and by applying a logistic regression including treatment group, MMR status at 24 weeks and their interaction as covariates. Treatment group will be included in this summary table. The odds ratios between treatment groups with 95% confidence intervals will be reported, for each category of MMR status at 24 weeks and overall. If the interaction of treatment by MMR status at 24 weeks is significant (e.g. when $p < 0.1$), overall odds ratio for treatment will not be reported.

Efficacy Analysis on Switch Analysis Set

Efficacy analyses on the Switch Analysis Set will be performed at the time of the 96-week analysis. Unless otherwise specified, endpoints are defined and analyzed similarly as specified in Sections 2.5, 2.6, and 2.7 on Switch Analysis Set, but with baseline, FD, LD, and EoT replaced by baseline_switch, FD_{switch}, LD_{switch}, and S-EoT. The below are the efficacy endpoints to be analyzed:

- MMR rate at and by all protocol-planned visits.
- CCyR rate at and by all protocol-planned visits.
- Time to MMR
- Duration of MMR
- Time to CCyR
- Duration of CCyR
- Time to Treatment Failure

The analysis of time-to-event endpoints will be conducted only if at least 5 events are observed.

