3.1 Primary analysis

To test the null hypothesis that the MMR rate at 24 weeks is equal in the two treatment arms, based on two-sided 5% level of significance and with 90% power, 222 patients will be needed in total (i.e. 148 patients in the asciminib arm and 74 patients in the bosutinib arm based on 2:1 randomization allocation). The calculations were made using the software package PASS (2008).

It is assumed that asciminib leads to a 20% improvement in the MMR rate at 24 weeks over bosutinib from 15% to 35% which corresponds to an odds ratio of 3.05. The assumed bosutinib MMR rate of 15% at 24 weeks is based on previous trials evaluating bosutinib therapy ([Kuoury et al. 2012], [Gambacorti-Passerini et al. 2014], [García-Gutiérrez et al. 2015]).

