3.2 Power for analysis of key secondary variables

If the primary analysis of MMR rate at 24 weeks is statistically significant, then the key secondary endpoint MMR rate at 96 weeks will be tested, with the overall alpha controlled at the 5% two-sided level using a gatekeeping strategy.

Table 3-1 below summarizes the treatment effects of the key secondary endpoint which can be detected with 80% and 90% power, based on the specified assumptions regarding the bosutinib effect. The calculations were made using the software package PASS (2008).

Table 3-1 Detectable effect sizes for key secondary endpoint

Endpoint	Anticipated effect with bosutinib	2-sided alpha	Power	Detectable effect size [§]
MMR rate at 96 weeks	30% [*]	0.05	90%	≥ 23%
			80%	≥ 20%

*: [Gambacorti-Passerini et al. 2014], Figure 1D.

§: Absolute difference from the anticipated effect with bosutinib.

For MMR rate at 96 weeks, if the anticipated effect with bosutinib is 30%, then the given sample size with 2-sided alpha=0.05 would allow to detect an absolute difference of at least 23% (i.e. MMR rate at 96 weeks with asciminib is at least 53%) for 90% power and of at least 20% (i.e. MMR rate at 96 weeks with asciminib is at least 50%) for 80% power.

4 Change to protocol specified analyses

Pharmacokinetic analysis set: Removal of the condition related to vomiting to consider a concentration evaluable as the occurrence and time of vomiting is not collected in the CRF.

The estimand language was implemented in sections 2.5 and 2.6. Then, the PPS and analyses based on PPS were removed.

The subgroup considering historical BCR-ABL1 mutations was removed as not considered clinically relevant.

A definition for loss of CHR was provided.

Definition of loss of MMR: removed any reference to confirmation of CHR and CCyR as confirmation of CHR and CCyR was not mandated by protocol and was therefore not performed in practise.

The following analyses were added:

ECOG status, time to event analyses for duration of MMR and CCyR, exposure adjusted AE incidence and yearly AE incidence, COVID-19 related sensitivity analyses.

5 Appendix

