5.6.3 Other analyses

Mantel-Haenszel common odds ratio

To obtain Mantel-Haenszel estimates of the common odds ratio and the corresponding 95% confidence interval in exploratory analyses, it requires SAS procedure FREQ with CMH and RELRISK options in the TABLES statement.

Logistic Regression

Odds ratio will be used as a measure of association between treatment and response in exploratory analyses ([Section 2.14](#)). The odds ratio will be derived from the logistic regression model (implemented using SAS procedure LOGISTIC, with treatment specified as an explanatory variable in the CLASS statement) which allows for including not only the stratification factor but also for adjustments for other covariates (both categorical and continuous). The odds ratio will be presented with 95% Wald confidence limits.

In cases where an exact test has been used to compare response rates, the odds ratio should be determined using exact logistic regression, and the odds ratio presented with exact 95% confidence limits. In these cases, SAS PROC LOGISTIC with EXACTONLY option will be used.

Kaplan-Meier estimates

An estimate of the survival function in each treatment group will be constructed using Kaplan-Meier (product-limit) method as implemented in PROC LIFETEST with METHOD=KM option. The PROC LIFETEST statement will use the option CONFTYPE=LOGLOG.

Median survival for each treatment group will be obtained along with 95% confidence intervals calculated from PROC LIFETEST output using the method of [\[Brookmeyer and Crowley 1982\]](#). Kaplan-Meier estimates of the survival function with 95% confidence intervals at specific time points will be summarized. The standard error of the Kaplan-Meier estimate will be calculated using Greenwood's formula [\[Collett 1994\]](#).

Hazard ratio

Hazard ratio will be estimated by fitting the Cox proportional hazards model using SAS procedure PHREG (with TIES=EXACT option in the MODEL statement).

A stratified unadjusted Cox model will be, i.e. the MODEL statement will include the treatment group variable as the only covariate and the STRATA statement will include stratification variable(s). Hazard ratio with two-sided 95% confidence interval will be based on Wald test.

Cumulative incidence

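### The exploratory treatment-by-mutation and treatment-by-early-response logistic models have no rule for a cell with 0% or 100% response, and the exact fallback in SAP 5.6.3 is not clearly linked to them.

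*Combined protocol and SAP*

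**What the plan says.** References are to SAP addendum 1.0 (14-Oct-2020), the last version shown in full.

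- **Section 2.13.1** examines Week 1 Day 1 mutation status against MMR and CCyR at and by 24 and 96 weeks by contingency tables and by "applying a logistic regression including treatment group, Week 1 Day 1 BCR-ABL1 gene mutation and their interaction as covariates". The same analysis is planned for new post-baseline mutations. On reporting: "The odds ratios between treatment groups with 95% confidence intervals will be reported, for each biomarker category and overall". The overall figure is dropped if the interaction is significant, with p<0.1 given as an example.
- **Section 2.14** uses the same form for MMR at Week 24 as a predictor of MMR at 48 and 96 weeks: "If the interaction of treatment by MMR status at 24 weeks is significant", the overall odds ratio is not reported.
- **Section 5.6.3**, referring to the exploratory odds ratios of Section 2.14, prescribes PROC LOGISTIC and states: "The odds ratio will be presented with 95% Wald confidence limits". Exact logistic regression replaces this when response rates were compared by an exact test. That exact test is defined in Section 5.6.1 as the small-count alternative to the primary CMH test.

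Neither 2.13.1 nor 2.14 names an estimator, an interaction test, a minimum cell count or a rule for separation. The 15-patient minimum in Section 2.2.1 is stated for the subgroups listed there.

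**The concern.** Two binary factors and their interaction give four parameters for four cells. Each category odds ratio is therefore the raw cross-product ratio of its own two cells. One cell with 0% or 100% response sends the estimate to zero or infinity and its Wald standard error to infinity.

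Two things are then at stake. The category odds ratio and interval that the plan asks for cannot be reported. In addition, the interaction p-value acts as a gate: a Wald p near 1 would let the overall odds ratio through when the two categories differ most. Without a written rule, the remedy would be chosen after the data are seen. Section 2.13 says that the BCR-ABL1 mutation results go into the clinical study reports.

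**Working it through.** **1. The plan's own figure.** Section 3.1 states: "based on two-sided 5% level of significance and with 90% power, 222 patients will be needed in total". For 15% versus 35% at 2:1, the pooled-variance formula without continuity correction gives 73.2 in the smaller arm, rounded up to 74. Then 74 + 148 = 222, which agrees. The odds ratio is (0.35/0.65)/(0.15/0.85) = 3.05, also as stated. The cell sizes below use "148 patients in the asciminib arm and 74 patients in the bosutinib arm based on 2:1 randomization allocation".

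**2. Week 1 Day 1 mutations.** The documents give no mutant share, so 8%, 12% and 20% are assumed. These give 12/6, 18/9 and 30/15 mutants (asciminib/bosutinib). For one cell, P(0% or 100%) = p^n + (1−p)^n. For at least one of the two mutant cells it is 1 − (1−P_A)(1−P_B).

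| Assumed MMR in mutants | 12/6 | 18/9 | 30/15 |
|---|---|---|---|
| 35% vs 15% (planned, Week 24) | 38% | 23% | 9% |
| 25% vs 10% (assumed lower rates) | 55% | 39% | 21% |
| 50% vs 30% (Week 96, 80% power row of Table 3-1) | 12% | 4% | 0.5% |

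For the first entry: bosutinib 0.15^6 + 0.85^6 = 0.377, asciminib 0.35^12 + 0.65^12 = 0.006, combined 0.381.

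**3. New post-baseline mutations.** Table 2-8 samples patients who are wild type at baseline again only at end of treatment; Table 1-1 adds confirmed loss of MMR. An end-of-treatment visit before Week 96 is non-response (2.6.1). Confirmed loss of MMR and new T315I or V299L are treatment failures (5.4.4). The new-mutation row will therefore hold few Week 96 responders by construction. With an assumed 5% MMR:

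- 6 and 4 cases: 0.95^6 = 0.735 and 0.95^4 = 0.815. At least one arm empty: 1 − 0.265 × 0.185 = 95%. Both empty: 0.735 × 0.815 = 60%.
- 10 and 6 cases: 0.599 and 0.735. At least one empty: 89%. Both empty: 44%.

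**4. Early-response model.** At the planned rates about 0.15 × 74 = 11 bosutinib patients are in MMR at Week 24 and 63 are not. To reach 30% at Week 96 (22.2 patients) with 80% to 95% of the 11 retained, the 63 need a late rate of (22.2 − 11r)/63, or 21% to 19%. The chance that none of the 63 responds is then below 0.00001. The realistic problem is the opposite cell, all 11 keeping MMR. With assumed retention of 80%, 90% and 95%, r^11 = 9%, 31% and 57%.

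**5. What separation does to the interaction test.** This illustration was chosen to be extreme: wild type 45/130 vs 10/65, mutants 0/18 asciminib vs 3/9 bosutinib.

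- Wald: p is 0.68, 0.94, 0.98 and 0.998 after 8, 12, 15 and 20 Newton steps. It tends to 1, and any printed value depends only on when iteration stops.
- Likelihood ratio: p = 0.0007.
- Firth: interaction estimate −4.0 (SE 1.7).
- The model without interaction gives an overall odds ratio of about 2.1 in favour of asciminib, although the mutants go the other way.
- With 1/18 in place of 0/18 the Wald p is 0.014. The milder data trip the p<0.1 rule and the more extreme data pass it.

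A simulation of 4,000 trials agrees (assumed: 15% mutants, MMR 50% vs 3% in mutants and 35% vs 15% in wild type). Separation occurred in 70% of trials. The interaction reached p<0.1 in 3% by Wald and 61% by likelihood ratio. Among separated trials Wald never did, and likelihood ratio did in 80%.

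**The case against.** The strongest reply is that the SAP nowhere prescribes a Wald interaction test. A reader might infer one from 5.6.3, but that sentence concerns limits for odds ratios and follows a reference to Section 2.14, so carrying it to 2.13.1 is itself an inference. The p<0.1 threshold is only an example. With a likelihood-ratio test the rule works when a single cell is empty. This stands: the failure of the gate is conditional on a Wald test. What remains is that no test is named and the only stated interval method is Wald.

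It can also be said that the exact-logistic clause already covers sparse data. Its trigger is an exact comparison of response rates, and no such comparison accompanies these models. The link is unclear, which is weaker than saying the clause is excluded.

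Three further readings go beyond the documents:

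- **Empty cells will be common throughout.** That depends on a mutant share the documents do not give. At Week 96 with 50% vs 30% the chance is at most 12% over the assumed range.
- **The early-response model will lack responders.** Under the plan's rates the risk there is a full cell.
- **The new-mutation analyses would hide a strong interaction.** In 44% to 60% of the assumed cases both arms are empty, and the interaction is then not estimable.

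Finally, 2.13.1 and 2.14 also require contingency tables, so a pattern such as 0/18 vs 3/9 would be visible, and Section 2.13 calls the biomarker work hypothesis-generating. That limits the consequence but does not supply the missing rule.

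**Conclusion.** The point holds as a gap in the exploratory models: they are saturated, have no provision for a 0% or 100% cell, and have an exact fallback that is not clearly tied to them. For Week 1 Day 1 mutations at Week 24 the chance of such a cell is about 9% to 38%, given 8% to 20% mutants and 35% vs 15%. It is 21% to 55% if mutants respond at 25% vs 10%, and 0.5% to 12% at Week 96 with 50% vs 30%. For new mutations it is about 89% to 95% under the assumed counts and 5% response. For the early-response model, a full bosutinib cell has a chance of 9% to 57% over the assumed retention range.

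When a single such cell occurs, its category odds ratio and Wald limits are unusable under maximum likelihood; with both arms empty or both full, that level's odds ratio is not estimable. The interaction gate fails only if the test is Wald. A reader might infer that the trial's conclusions are at risk. The documents do not support that: the primary and key secondary comparisons are CMH tests and do not use these models.

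**What to change.** In 2.13.1, 2.14 and 5.6.3:

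- Fit these interaction models with Firth's penalised likelihood (the FIRTH option of the MODEL statement in PROC LOGISTIC) and report profile-likelihood limits.
- Base the p<0.1 rule on the penalised likelihood-ratio test.
- Where a factor level has no responders, or only responders, in both arms, show the contingency table only and give no odds ratio for that level. Firth, which adds 0.5 to each cell in a saturated model, would otherwise print 4.5/6.5 = 0.69 for 0/6 vs 0/4 and 6.5/10.5 = 0.62 for 0/10 vs 0/6. Those values reflect group size alone.
- Label the change post hoc for Week 24 results already analysed, since addendum 1.0 is dated after database lock for the primary analysis.

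The cost is one procedure option and a few sentences in the SAP. The downside is slight shrinkage of the odds ratios where the cells are not degenerate.

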2.7.3 Handling of missing values/censoring/discontinuations

MMR rates at specific time points: Patients discontinuing the randomized treatment prior to a specific time point due to any reason or patients without an available assessment at that time point will be considered as non-responders for that time point.

MMR rates by specific time points:

Patients without any documented response for which an evaluable response assessment was never provided will be considered as non-responders for the period of time up to that time point.

Molecular response at specific time points: The category “Missing” will be assigned to

- Ongoing cases, i.e. patients without assessment at the specific time point who have not discontinued study treatment and have not been treated sufficiently long for a specific time point
- Discontinued due to progressive disease/death prior to a specific time point
- Discontinued due to other reasons prior to a specific time point
- **Molecular response category by specific time points:** The category “Missing” will be assigned to patients for whom an evaluable response assessment was never provided.

Time to MMR: For patients in the FAS who have not experienced any MMR, the time will be censored as follows in the Kaplan-Meier analysis:

- If a patient does not achieve the specified response before the cut-off date for the analysis, censoring time will be the last molecular assessment (PCR) date on treatment prior to the cut-off date or the EoT visit, whichever comes first.
- If a patient discontinues study treatment prior to achieving a response for a reason other than disease progression or death, then the patient will be censored at the last molecular assessment (PCR) date on treatment prior to the cut-off date or the EoT visit, whichever comes first.
- If a patient discontinues study treatment prior to achieving a response due to progression or death, then the censoring time will be set to the longest follow-up time in the treatment group, that is, consider the response is impossible to reach.
- In case no on-treatment response assessment was performed, the patient will be censored at day 1.

Duration of MMR: For patients in the MMR responder set who have not experienced any event (loss of MMR, progression to AP/BC, or CML-related death), the duration will be censored at the last molecular assessment (PCR) date on treatment.

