CCyR rates at specific time points: Patients discontinuing the randomized treatment prior to a specific time point due to any reason will be considered as non-responders for that time point.

CCyR rates by specific time points: This will be handled similarly as MMR, but with CCyR instead.

Cytogenetic response at specific time points: This will be handled similarly as molecular response category.

Cytogenetic response category by specific time points: This will be handled similarly as molecular response category.

Time to CCyR: For patients in the CCyR analysis set who have not experienced any CCyR, the time will be censored in the same manner as Time to MMR.

Duration of CCyR: For patients in the CCyR responder set who have not experienced any event (loss of CCyR, progression to AP/BC, or CML-related death) the duration will be censored at the last cytogenetic assessment date on treatment or the last PCR evaluation on treatment indicating MMR, whichever is the latest.

TTF: For patients in the FAS who have not reached treatment failure, their TTFs will be censored at the time of their last study assessment (PCR, cytogenetic, hematologic or extramedullary) before the cut-off date.

PFS: For patients who have not experienced an event (disease progression to AP/BC or death from any cause), their PFS times will be censored at the date of last study assessment (PCR, cytogenetic, hematologic or extramedullary) before the cut-off date, regardless of subsequent intake of treatment(s) after randomization.

OS: Patients who are alive at the time of the analysis data cutoff date will be censored at the date of last contact (see [Section 2.1.1](#)) before the cut-off date, regardless of subsequent intake of treatment(s) after randomization.

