5.4.4 Treatment Failure

The following events will constitute 'treatment failure', and are based on the ELN criteria ([Baccarani et al 2013](#)) defining failure of a second line treatment adapted to include discontinuation of randomized treatment as an event:

- No CHR or > 95% Ph+ metaphases at three months after initiation of therapy or thereafter
- BCR-ABL1 ratio > 10% IS and/or > 65% Ph+ metaphases at six months after initiation of therapy or thereafter
- BCR-ABL1 ratio > 10% IS and/or > 35% Ph+ metaphases at 12 months after initiation of therapy or thereafter
- Loss of CHR, CCyR or PCyR at any time after initiation of therapy
- Detection of new BCR-ABL1 mutations which potentially cause resistance to study treatment (T315I and V299L), at any time after initiation of therapy
- Confirmed loss of MMR in 2 consecutive tests
- New clonal chromosome abnormalities in Ph+ cells: CCA/Ph+: at any time after initiation of therapy

- Discontinuation from randomized treatment for any reason* (Note that Reason for treatment discontinuation="completed" doesn't indicate a premature treatment discontinuation)

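### Under the SAP schedule, baseline wild-type patients are re-sequenced only when they stop treatment or lose response, so the planned association of new BCR-ABL1 mutations with Week 48 and Week 96 response is biased towards mutation meaning no response

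*Combined protocol and SAP*

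**What the plan says.** All references are to the SAP text of addendum 1.0 (14-Oct-2020).

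- **The analysis (Section 2.13.1).** Two post-baseline models are planned. The first concerns "the relationship between post-baseline new BCR-ABL1 mutation (with or without new mutation) up to 48 weeks and outcome data", the outcomes being MMR (FAS) and CCyR (CCyR Analysis Set) at Weeks 48 and 96. The second concerns "the relationship between post-baseline new BCR-ABL1 mutation (with or without new mutation) up to end of treatment and outcome data", with Week 96 outcomes only. Each is a contingency table plus a logistic model with treatment, mutation and their interaction. Treatment odds ratios are reported per mutation category and overall, and the overall one is withheld if the interaction is significant (p < 0.1 is given as the example). The only caution concerns multiple comparisons.
- **The sampling (Section 2.13).** Table 2-8 gives Sanger sequencing as "W1D1 pre-dose and end of treatment. If mutation is present at baseline, then also every 12 weeks after baseline". The objective in the same section adds one trigger: "upon confirmed loss of molecular response and/or at end of treatment".
- **The response rules.** For MMR at a visit (Section 2.7.3), "Patients discontinuing the randomized treatment prior to a specific time point due to any reason or patients without an available assessment" are non-responders. For CCyR, "Patients discontinuing the randomized treatment prior to a specific time point due to any reason will be considered as non-responders for that time point". Section 2.6 counts stopping, or meeting any failure criterion, before Week 96 as non-response. Section 5.4.4 lists confirmed loss of MMR as treatment failure, and also "Detection of new BCR-ABL1 mutations which potentially cause resistance to study treatment" (T315I and V299L). Section 2.1.1 leaves efficacy assessments after failure or after the end-of-treatment visit out of the efficacy analyses, apart from PFS and OS.
- **The population (Section 2.13).** Biomarker analyses use FAS patients who have biomarker data. The status of a patient never re-sequenced is not defined.

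**The concern.** The explanatory variable is a detected mutation, and detection needs a sample. In baseline wild-type patients the sample is taken because of an event that the response rules already count against the patient. Patients who stay on treatment in response, the ones who could show a new mutation alongside a response, are not sampled. The model would then report an association that comes at least partly from the sampling schedule.

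Three outputs are at stake: the odds ratio for mutation, the treatment odds ratio among patients with a new mutation (few responders in either arm), and the interaction test that decides whether the overall treatment odds ratio is shown. In addition, an arm with more early stops gets more end-of-treatment sequencing, and so more opportunity to record a new mutation.

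**Working it through.** The SAP states no figure for this analysis, so there is none to reproduce. The only figure borrowed is the planned total of 222 (Section 3.1). It reproduces as 74 + 148 from 15% versus 35%, two-sided 5%, 90% power, 2:1, with pooled variance and no continuity correction. Nothing below depends on it beyond its use as a sample size.

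**Step 1: follow a baseline wild-type patient up to the Week 48 visit.**

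1. Re-sequencing needs an end of treatment or a confirmed loss of response (Section 2.13).
2. Section 2.1.1 plans at least 96 weeks of treatment for patients who do not switch, and a switch follows bosutinib failure. An end of treatment before Week 48 is therefore never a completion. It makes the patient a non-responder at Weeks 48 and 96 (Sections 2.7.3 and 2.6).
3. Confirmed loss of MMR is failure (Section 5.4.4). Later assessments are excluded (Section 2.1.1), and missing ones count as non-response.
4. So a recorded new mutation almost always comes with non-response at both visits.

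**Step 2: expected table in wild-type patients with no true association.** Assumed inputs: 190 wild-type patients, 45% stopped or failed by Week 48, 45% MMR in the rest, 10% true new mutation unrelated to response, untested patients coded as without, and the narrow exceptions ignored.

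- Stopped or failed: 190 × 0.45 ≈ 86. Responders: (190 − 86) × 0.45 ≈ 47.
- Detected mutations: 86 × 0.10 ≈ 9, with 0 responders. Without: 47 responders and 190 − 9 − 47 = 134 non-responders.
- Odds ratio, adding 0.5 to each cell: (0.5 × 134.5) / (9.5 × 47.5) = 0.15.
- With everyone sampled, about 5 of 47 responders and 14 of 143 non-responders would show a mutation: (5 × 129) / (14 × 42) = 1.10, which is 1 apart from rounding.
- Varying the stopped share over 30–60% and true mutation over 5–20% gives 0.08 to 0.34.

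**Step 3: the planned population, which includes baseline mutants.** Simulation with 222 patients, 45% MMR among those not stopped or failed, true odds ratio 1, 1,000 runs per setting. Baseline mutants (10% or 20%) are always sampled, the others only if stopped or failed (30% or 50%); untested patients count as without.

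| True new mutation | Median odds ratio | Rejection at nominal 5% (Fisher) |
|---|---|---|
| 5% | 0.32–0.47 | about 1% |
| 10% | 0.21–0.42 | 10–19% |
| 20% | 0.18–0.36 | 37–70% |

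**Step 4: new mutation up to end of treatment against Week 96 response.** Assumed: 13% baseline mutants, 55% stopped or failed by Week 96, 60% MMR in the rest, 10% true new mutation. The quantity varied is the share of patients not otherwise sampled who nevertheless have an end-of-treatment sample.

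| Share sampled | Median odds ratio | Rejection at nominal 5% |
|---|---|---|
| None | 0.21 | 40% |
| Half | 0.65 | 10% |
| All | 1.03 | 4.3% |

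At the LPFT + 96 weeks cut-off (Section 2.1), Week 96 responders still on treatment have no end-of-treatment sample, so the first row is the nearer one. It is not exact, because patients who stopped between Week 96 and the cut-off do have a sample. At an end-of-study-treatment analysis the situation moves towards the last row.

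**Step 5: the undefined group.** Steps 2 to 4 code untested patients as without. If they are excluded instead, wild-type patients contribute almost only non-responders and nearly every responder is a baseline mutant. A difference in new-mutation frequency between wild-type patients who stopped and baseline mutants is then read as an association with response, and the model has no term for baseline mutation. Neither coding cures the problem.

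**The case against.** The strongest case against has five parts.

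- **Complete separation is not guaranteed.** A reader might infer that wild-type patients with a new mutation have zero responders by rule and that the mutation coefficient cannot be estimated. The documents do not support that. End-of-treatment assessments are mapped to visits, and the Week 48 windows are Days 296–379 for PCR and Days 254–421 for cytogenetics. A patient stopping inside the window could have a responding assessment mapped to Week 48, and Section 5.5.1 classifies by the assessment in the window. A marrow in CCyR taken before confirmed loss of MMR could also count. And the planned models use the FAS or the CCyR Analysis Set, where baseline mutants sampled every 12 weeks can supply responders with a new mutation. These exceptions stand. They are narrow, and they turn a certain result into a biased one.
- **Coding of untested patients.** A reader might infer that they default to without. The SAP does not say so, and its mutation summaries carry a missing/unknown group. This stands as a correction, but Step 5 shows that excluding them does not help.
- **The second model.** An end of treatment after Week 96, or one coded as completed, does not define Week 96 non-response. This stands: that model is only partly affected.
- **Unseen text.** Table 2-8 omits the loss-of-response trigger, so it is not exhaustive, and the main protocol sections on mutation sampling are not in the material available. The point therefore rests on the SAP schedule.
- **Exploratory status.** Section 2.13 calls these analyses hypothesis-generating. That lowers the severity. It does not make the models informative, and the results are to go into the clinical study reports.

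**Conclusion.** The point holds as a bias in two exploratory models, and it is minor. For the Week 48 model, wild-type patients' new mutations are recorded almost only together with non-response. With untested patients coded as without, the estimate is pulled towards mutation meaning no response. The size depends on the share of baseline mutants, the stopping rate and the true mutation frequency, none of which the documents give: over the ranges assumed, median odds ratios of 0.18 to 0.47 where the true value is 1, and false rejection from about 1% to 70%.

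Those figures come from a two-by-two table without treatment arms and with the exceptions ignored, so they illustrate size and do not predict the fitted model. If untested patients are excluded, a distortion remains but has not been sized, and its direction depends on how mutation frequency differs between the groups sampled. A new T315I or V299L, being itself a failure event, also pushes towards non-response, in baseline mutants too. The end-of-treatment model is affected mainly at the LPFT + 96 weeks cut-off. The primary and key secondary tests and the Week 1 Day 1 mutation analysis are unaffected.

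**What to change.** In Section 2.13.1, replace the two post-baseline logistic analyses and their per-category treatment odds ratios with a descriptive table of new mutations by arm:

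- denominator: patients with at least one post-baseline sequencing result;
- not tested: shown as a separate category;
- split by sampling trigger: end of treatment for lack of efficacy, end of treatment for other reasons, confirmed loss of MMR, scheduled 12-weekly sample.

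The section already plans a by-arm summary of new mutations, so this mainly changes its denominator and layout. Limit any association analysis to baseline-mutant patients sampled every 12 weeks: take mutation status up to a landmark visit among those still on treatment, relate it to response at a later visit, and label it small and exploratory. Keep the Week 1 Day 1 analysis as planned.

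The cost is SAP wording and the loss of two pre-specified exploratory model outputs. No new samples are needed.
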